7.3.6.2. Known-Groups Validity

The purpose of the known-groups validity is to assess the degree to which the measure can distinguish among groups of subjects hypothesized to be different in concepts of interest. In the case of the RESCUE trial there are several concepts of interests.

The known-group analysis will accordingly refer to the following three grouping criteria:

- Hemoglobin: High (≥ 11 g/dL) Vs. Low (< 11 g/dL)
- CKD Stages: 3 vs. 4 or 5
- PGIS: groups will be defined at baseline by PGIS (None, Mild, Moderate, Severe)

For the PGIS classification, adjacent groups may be combined if the sample size of a particular category is <10 patients.

Document : /Users/████████/Dropbox (Corvidia Tx)/Corvidia Tx Team Folder/Assets/COR-001/Clinical/RESCUE (COR-001-02)/Manuals & Plans/PRO
PAP/Corvidia_RESCUE_PAP_FinalV2.0_24APR2020.docx

Author: ██████████ Version No: V2.0
Version Date: 24APR2020

Template No.: ██████████ Reference: ██████████

Effective Date: 01Dec2018

Copyright © 2018 ██████████ All rights reserved. The contents of this document are confidential and proprietary to ██████████ and its subsidiaries. Unauthorized use, disclosure or reproduction is strictly prohibited.

Known-group validity for the Hemoglobin and CKD Stage groups will be tested with a group mean t-test with alpha = 0.05 level for the CARES and PROMIS Fatigue total and subscale scores.

PGIS groups will serve as the independent variable in an analysis of variance (ANOVA) with alpha = 0.05 level, and the CARES and PROMIS Fatigue total and subscale scores will serve as dependent variables. Kruskal-Wallis test, a non-parametric alternative to ANOVA, will be conducted if group data for any group criteria are not reasonably balanced.

Box-plots of the CARES and PROMIS Fatigue total and subscale scores for each group will be also presented to highlight the degree of separation and heterogeneity between the scores' distributions across groups.

7.3.7. SENSITIVITY TO CHANGE

Sensitivity to change is the ability of an instrument to measure change in a state regardless of whether it is relevant or meaningful to the decision maker. Sensitivity to change will be examined using one-way analysis of covariance (ANCOVA). Subjects with baseline and Visit 7 data will be included in the analysis.

The dependent variable will be the change from baseline to Visit 7 in the CARES and PROMIS Fatigue total and subscale scores. The responder group will be formed using the PGIC and PGIS scores. The model will include the "responder" factor as a fixed factor and the analysis will be controlled for the baseline PRO scores. Separate models will be considered for each CARES and PROMIS Fatigue total score and EFA-based scales.

Using the PGIC, the following three groups will be created using the PGIC score at Visit 7:

- 'Improved' group will include those participants who answered "Very much better", "Moderately better", and "A little better".
- 'No change' group will include those participants who answered 'No change'.
- 'Worsened' group will include those participants who answered "Very much worse", "Moderately Worse", and "A little worse".

Using the PGIS, the following three groups will be created using the PGIS score at Visit 7:

- Improved is defined as patients with an improvement on their PGIS of at least one level from baseline to Visit 7
- Worsening is defined as patients with a worsening of at least one level from baseline to Visit 7
- Unchanged is defined as patients with same PGIS score at Visit 7 and at baseline

The analysis will be performed on groups with ≥ 10 patients and adjacent groups may be

Document : /Users/[REDACTED]/Dropbox (Corvidia Tx)/Corvidia Tx Team Folder/Assets/COR-001/Clinical/RESCUE (COR-001-02)/Manuals & Plans/PRO
PAP/Corvidia_RESCUE_PAP_FinalV2.0_24APR2020.docx

Author: [REDACTED] Version No: V2.0

Version Date: 24APR2020

Template No.: [REDACTED] Reference: [REDACTED]

Effective Date: 01Dec2018

Copyright © 2018 [REDACTED] All rights reserved. The contents of this document are confidential and proprietary to [REDACTED] and its subsidiaries. Unauthorized use, disclosure or reproduction is strictly prohibited.

combined if there are <10 patients. Separate models will be considered for each "responder" group definition.

The model will present least squares (LS) mean estimates, standard errors, 95% confidence intervals (CIs) and p-values. The analysis of variance will be conducted using the PROC GLM procedure in SAS.

7.3.8. MEANINGFUL CHANGE

Individual-level thresholds of meaningful change will be explored. To identify patients who experienced a significant improvement in their symptoms over the course of treatment, a responder definition will be determined to characterize a meaningful change in the scores of the CARES and PROMIS Fatigue measures. Anchor-based and distribution-based methods, as well as graphical displays, will be used to support the interpretation of possible treatment benefits as reflected in the CARES and PROMIS Fatigue scores. These approaches will help characterize the amount of change important to patients on these dimensions (as recommended in the FDA PRO guidance [FDA 2009; FDA 2019]).

Thresholds will be estimated for the CARES and PROMIS Fatigue total score and scales and/or subscales obtained from the EFA.

7.3.8.1. Distribution-Based Approach

The following two distribution-based approaches will be applied to the baseline CARES and PROMIS Fatigue total scores and EFA-based scales.

One-half standard deviation (SD):

SD of Baseline PRO scores will be computed and divided by 2

1 standard error of measurement (SEM):

$$SEM = SD_{baseline} * \sqrt{1 - r_{xx}}$$

where $SD_{baseline}$ = SD at Baseline and r_{xx} = the reliability (internal consistency) of PRO scale score at Baseline

7.3.8.2. Anchor-Based Approach

In the anchor-based approach, the PGIS and PGIC will be used. Specifically, subjects will be classified in groups to provide a clearer difference between subjects who have and have not experienced meaningful change according to the anchors. Meaningful change thresholds will be derived using each level of the PGIS and PGIC. If the sample size within a response category is too small, grouping of the response categories will also be considered as indicated in Table 2.

Document : /Users/[REDACTED]/Dropbox (Corvidia Tx)/Corvidia Tx Team Folder/Assets/COR-001/Clinical/RESCUE (COR-001-02)/Manuals & Plans/PRO
PAP/Corvidia_RESCUE_PAP_FinalV2.0_24APR2020.docx

Author: [REDACTED] Version No: V2.0

Version Date: 24APR2020

Template No.: [REDACTED]

Reference: [REDACTED]

Effective Date: 01Dec2018

Copyright © 2018 [REDACTED] All rights reserved. The contents of this document are confidential and proprietary to [REDACTED] and its subsidiaries. Unauthorized use, disclosure or reproduction is strictly prohibited.

Table 2 Categories for change in PGIS and PGIC

Instrument	Category	Definition
PGIS at Visit 7	Un-collapsed Categories	
	Improved 3 categories	CFB =-3
	Improved 2 categories	CFB =-2
	Improved 1 category	CFB =-1
	No Change	CFB =0
	Worsened 1 category	CFB =+1
	Worsened 2 categories	CFB =+2
	Worsened 3 categories	CFB =+3
	Collapsed Categories	
	Improvement	CFB \leq -1 point
PGIC at Visit 7	No Change	CFB=0
	Worsening	CFB \geq +1 point
	Un-collapsed Categories	
	Very much improved	Rating "very much better"
	Much improved	Rating "moderately better"
	Minimally improved	Rating "a little better"
	No change	Rating "no change"
	Minimally worse	Rating "a little worse"
	Much worse	Rating "moderately worse"
	Very much worse	Rating "very much worse"
	Collapsed Categories, 5 categories	
	Very much improved	Rating "very much better"
	Improvement	Rating of "a little better" and "moderately better"
	No change	Rating of "no change"
	Worsening	Rating of "a little worse" or "moderately worse"
	Very much worse	Rating "very much worse"
	Collapsed Categories, 3 categories	
	Improvement	Rating of "a little better", "moderately better" or "very much better"
	No change	Rating of "no change"
	Worsening	Rating of "a little worse" or "moderately worse" or "very much worse"

CFB=Change from baseline at Visit 7.

The change in the CARES total score and EFA based scales from baseline (average of Day -7 to Day -1) to the Visit 7 (average of daily measurements from day 78 to day 84) will be used in the anchor-based analyses.

Document : /Users/[REDACTED]/Dropbox (Corvidia Tx)/Corvidia Tx Team Folder/Assets/COR-001/Clinical/RESCUE (COR-001-02)/Manuals & Plans/PRO
PAP/Corvidia_RESCUE_PAP_FinalV2.0_24APR2020.docx

Author: [REDACTED] Version No: V2.0

Version Date: 24APR2020

Template No.: [REDACTED] Reference: [REDACTED]

Effective Date: 01Dec2018

Copyright © 2018 [REDACTED] All rights reserved. The contents of this document are confidential and proprietary to [REDACTED] and its subsidiaries. Unauthorized use, disclosure or reproduction is strictly prohibited.

The same procedure will be applied to the *PROMIS Fatigue* total score and EFA-based scales using the matching 7-day recall measurement at baseline and Visit 7.

The adequacy of the anchors proposed above is explored with the Spearman correlations between the change from baseline to Visit 7 in CARES and *PROMIS Fatigue* total score and EFA-based scales. If the correlation coefficient >0.30, it will be emphasized in the interpretation of the results.

The following descriptive analyses will be conducted:

- Descriptive statistics for changes in the CARES total score and EFA-based scales from baseline (average of Day -7 to Day -1) to the Visit 7 (average of day 78 to 84). Descriptive statistics will be conducted for all categories as described in Table 2 Categories for change in PGIS and PGIC
- Descriptive statistics for changes in the *PROMIS Fatigue* total score and EFA-based scales from baseline to the Visit 7. Descriptive statistics will be conducted for all categories as described in Table 2 Categories for change in PGIS and PGIC
- Empirical cumulative distribution function plots (eCDF) and smooth Probability Density Functions (PDF) will be presented for each CARES and *PROMIS Fatigue* total score and EFA-based scales. These curves will be generated for all categories as described in Table 2.

Furthermore, two descriptive tables will be generated to display change in the PRO scores from baseline at Visit 7 by baseline PGIS. This will be conducted separately for patients who achieved a 1-category and 2-category PGIS decrease at Visit 7 from baseline. Change scores will be categorized by percentiles: 10th, 25th, median, 75th, and 90th. Three baseline PGIS categories (i.e., mild, moderate, severe) will be used for the 1-category PGIS decrease analysis, while two categories for baseline PGIS (i.e., moderate, severe) will be used for the 2-category PGIS decrease analysis.

The various estimates from the different streams of evidence (distribution methods and anchor methods,) will be tabulated and will be examined for convergence in an effort to triangulate onto a single threshold value that represents meaningful within-patient worsening/improvement. However, if this is not possible, a range of thresholds will be considered.

The results of the anchor-based analyses (original, un-collapsed PGIS categories) will be considered primary when making decisions regarding the clinically meaningful worsening and clinically meaningful improvement thresholds and will be supplemented with eCDF and PDF curves. The primary anchor to establish the meaningfulness of deterioration or improvement in patient scores over time is PGIS. Specifically, our *a priori* definition of clinically meaningful deterioration threshold will be change from baseline of +1 points on the PGIS; and the *a priori* definition of clinically meaningful improvement threshold will be change from baseline -1 points on the PGIS. However, the results from other analyses will also be considered.

Document : /Users/[REDACTED]/Dropbox (Corvidia Tx)/Corvidia Tx Team Folder/Assets/COR-001/Clinical/RESCUE (COR-001-02)/Manuals & Plans/PRO
PAP/Corvidia_RESCUE_PAP_FinalV2.0_24APR2020.docx

Author: [REDACTED] Version No: V2.0

Version Date: 24APR2020

Template No.: [REDACTED] Reference: [REDACTED]

Effective Date: 01Dec2018

Copyright © 2018 [REDACTED] All rights reserved. The contents of this document are confidential and proprietary to [REDACTED] and its subsidiaries. Unauthorized use, disclosure or reproduction is strictly prohibited.

The eCDF and ePDF plots will be visually examined to explore the data across a range of thresholds to ensure there is separation in the curves between the anchor groups and to examine the proportion of subjects experiencing up to that change at various thresholds. The eCDF displays a continuous plot of the change from baseline on the horizontal axis and the cumulative percent of patients experiencing up to that change on the vertical axis. The eCDFs and PDFs are mathematically related, displaying a distribution of PRO change score in different but complementary ways. eCDF plots optimally display the cumulative probabilities of change across the entire distribution and provide insight into the percentiles (e.g., median) of the PRO changes. PDF plots optimally display the moments of a distribution, such as the mean and variability.

7.3.9. CLASSIFICATION BY PATIENT SYMPTOMATOLOGY

One of the objectives of the interim blinded PRO data analysis of RESCUE data is to characterize patient symptomology, such that two classes of patients can be defined: low symptom burden (or non-symptomatic) and high symptom burden (or symptomatic).

The investigation will rely on quantitative approaches and will be also reviewed on the basis of qualitative considerations. This analysis will be exploratory in nature and iterative. Two methods will be considered:

- Cluster analysis (see section 7.3.9.1)
- Anchor analysis (see section 7.3.9.2)

The two symptom classes resulting from the above methods will be investigated for differential response patterns, by means of profile analysis (see section 7.3.9.3).

7.3.9.1. Cluster analysis

Cluster analysis will be performed to identify subgroups of patients who differ meaningfully on symptoms at baseline. The items and/or scales to be used for cluster analysis will be determined following an examination of the results of the descriptive analyses, item-to-item correlations, and EFA. The analysis will be performed separately for CARES and PROMIS Fatigue.

Two Cluster Analysis methods may be used: hierarchical clustering and k-means (or k-medoids) clustering. The initial cluster centres may be based on prototypical (clinically meaningful) "symptomatic", "non-symptomatic" etc. cluster centres. The algorithm from the k-means cluster analysis establishes an initial set of cluster means then assigns each case (i.e., patient) to the closest cluster mean. Alternative clustering algorithms may be used as appropriate given the features of the response. A two-cluster solution will be specified to aid in interpretation.

7.3.9.2. Anchor analysis

An external anchor, specifically PGIS will be used to inform the definition of a sufficiently

Document : /Users/████████/Dropbox (Corvidia Tx)/Corvidia Tx Team Folder/Assets/COR-001/Clinical/RESCUE (COR-001-02)/Manuals & Plans/PRO PAP/Corvidia_RESCUE_PAP_FinalV2.0_24APR2020.docx

Author: ██████████ Version No: V2.0

Version Date: 24APR2020

Template No.: ██████████ Reference ██████████

Effective Date: 01Dec2018

Copyright © 2018 ██████████ All rights reserved. The contents of this document are confidential and proprietary to ██████████ and its subsidiaries. Unauthorized use, disclosure or reproduction is strictly prohibited.

symptomatic patient. Specifically, the median baseline score for those who reported "mild", "moderate" or "severe" severity on the PGIS at screening will be used as a *threshold* for significant symptom burden. Patients will be further classified as "non-symptomatic" if their baseline score is < *threshold* and as "symptomatic" if their baseline score is \geq *threshold*.

The analysis will be performed separately for each scale/subscale of CARES and PROMIS Fatigue.

7.3.9.3. Profile analysis

The cluster analysis and the anchor analysis will identify patient profiles (symptom classes) based on shared symptoms at baseline. Differential response patterns will be assessed. Specifically, the following will be presented:

- A table with descriptive statistics for the PRO scores and a line graph with mean values and corresponding 95% confidence intervals (CI) by symptom classes and each visit (e.g., at baseline, Visit 4 and Visit 7).
- A table with descriptive statistics for the change from baseline in PRO scores by symptom classes and each visit (e.g., at baseline, Visit 4 and Visit 7).
- A cumulative distribution plot showing a continuous plot of the absolute change from baseline during the study for the PRO scores on the X-axis and the cumulative percent of patients experiencing that change on the Y-axis will be presented by symptom classes at Visit 7.

In addition, a mixed model for repeated measures (MMRM) will be used to evaluate change from baseline to Visit 7. The model will include variables for baseline hemoglobin (≥ 11 or < 11 g/dL), CKD Stage (3, 4 or 5), symptom class group, visit and treatment group-by-visit interaction as categorical fixed effects, baseline value and baseline-by-visit interaction will be included as covariates. The least squares means for each symptom class group, the least squares mean differences between symptom class groups along with the associated 95% confidence intervals (CIs) and p-values will be presented.

The analyses will be conducted using PROC MIXED in SAS. An unstructured covariance matrix will be used to model the within-subject correlation. The Kenward-Roger approximation will be used to adjust the denominator degrees of freedom. The analysis will be performed based on all observed post-baseline scores without any imputation of missing data. In the case when the MMRM fails to converge using an unstructured covariance matrix in any stage, a less stringent covariance matrix (e.g., autoregressive 1) will be used.

Document : /Users/[REDACTED]/Dropbox (Corvidia Tx)/Corvidia Tx Team Folder/Assets/COR-001/Clinical/RESCUE (COR-001-02)/Manuals & Plans/PRO
PAP/Corvidia_RESCUE_PAP_FinalV2.0_24APR2020.docx

Author: [REDACTED] Version No: V2.0

Version Date: 24APR2020

Template No.: [REDACTED] Reference: [REDACTED]

Effective Date: 01Dec2018

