4. ANALYSIS TIMING

The psychometric analysis will be performed at the same time as the primary analysis of the study, e.g., once all subjects complete Visit 7 (Week 13). [REDACTED] will perform the analysis using blinded data and data will be collapsed across treatment groups for the purpose of the psychometric analysis.

After the last subject completes the last visit, the final database will be cleaned and locked and this data will be used to repeat the derivation of the clinically meaningful threshold (see section 7.3.8). However, due to the impact of the Coronavirus Disease 2019 (COVID19) pandemic on the RESCUE clinical trial, this analysis will be performed only on the subset of patients with week 24 data. There are no plans to repeat further psychometric analyses on the final database.

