7. STATISTICAL METHODOLOGY

7.1. GENERAL CONSIDERATIONS

Summary statistics for continuous data will include the number of observations (N), mean, standard deviation (SD), median, first and third quartiles, minimum (min), and maximum (max). Categorical data will be described by the number (n) and percentage (%) of patients in each category. Missing and invalid observations will be tabulated as separate categories. The calculation of proportions will not include the missing/invalid category, unless specified otherwise.

Statistical comparisons will be made using two-sided tests at the $\alpha = 0.05$ significance level unless stated otherwise. Due to the exploratory nature of these analyses, no adjustments for multiplicity will be performed. For point estimates, 95% confidence intervals will be used.

The psychometric analysis will be performed on the pooled treatment arms.

Document : /Users/████████/Dropbox (Corvidia Tx)/Corvidia Tx Team Folder/Assets/COR-001/Clinical/RESCUE (COR-001-02)/Manuals & Plans/PRO
PAP/Corvidia_RESCUE_PAP_FinalV2.0_24APR2020.docx

Author: ██████████ Version No: V2.0

Version Date: 24APR2020

Template No.: ██████████ Reference: ██████████

Effective Date: 01Dec2018

Copyright © 2018 ██████████ All rights reserved. The contents of this document are confidential and proprietary to ██████████ and its subsidiaries. Unauthorized use, disclosure or reproduction is strictly prohibited.

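### The profile-analysis MMRM in the PAP contains a treatment-by-visit term on blinded, pooled data and lacks the class-by-visit term its own question needs

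*SAP*

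**What the plan says.** PAP v2.0 section 7.3.9 sorts patients into a low and a high symptom-burden class, by cluster analysis and by a PGIS anchor, and section 7.3.9.3 then compares the classes. The stated aim is that "Differential response patterns will be assessed". Besides descriptive tables and plots by class, "a mixed model for repeated measures (MMRM) will be used to evaluate change from baseline to Visit 7". Its terms are baseline hemoglobin category, CKD stage, "symptom class group, visit and treatment group-by-visit interaction as categorical fixed effects", plus the baseline value and baseline-by-visit as covariates. The inferential output is the class least squares means and "the least squares mean differences between symptom class groups", with confidence intervals and p-values.

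On the data to be used, PAP section 4 says that the analyst "will perform the analysis using blinded data and data will be collapsed across treatment groups". Section 7.1 adds: "The psychometric analysis will be performed on the pooled treatment arms". Section 7.3.9 itself places the symptom-class work within the interim blinded PRO analysis.

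For the anchor method, section 7.3.9.2 sets one cut for each scale: "the median baseline score for those who reported" mild, moderate or severe symptoms on the PGIS. Patients below the cut are labelled non-symptomatic; those at or above it are labelled symptomatic.

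**The concern.** Two defects sit in one phrase. First, a treatment-by-visit interaction cannot be fitted to data that carry no treatment variable. Supplying arm codes, even masked ones, would contradict the statements that the data are collapsed and the arms pooled. Clinical SAP section 4.1 also keeps the study team blinded until the final lock and gives the Week 13 analysis to an independent unblinded statistician.

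Second, the section asks whether the two classes respond differently over time and by Visit 7, but the model has no class-by-visit term. It forces the class difference to be the same at both post-baseline visits. A programmer who follows the text has to query the term or ask for codes, and would then report a class contrast that does not answer the question posed.

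**Working it through.** No figure in the plan needs reproducing. The check sets the passages side by side and then works out what the written model estimates.

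**Source of the sentence.** Clinical SAP section 3.4 gives its efficacy MMRM as hemoglobin category, CKD stage, treatment group, visit and treatment group-by-visit as fixed effects, with baseline and baseline-by-visit as covariates. The PAP sentence has the same terms in the same order. The only difference is that treatment group has become symptom class group in the main effect. The interaction was left unchanged, so treatment appears in an interaction without its own main effect. PAP v1.0 section 7.3.5.3 has the same model, so the v2.0 revision did not catch it.

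**What the single class effect estimates.** The post-baseline visits up to Visit 7 are Visits 4 and 7. Let d4 and d7 be the true class differences in change, s4 and s7 the residual SDs, and r their correlation. With both visits observed and an unstructured covariance, generalised least squares gives a common class effect of w4·d4 + w7·d7, where

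w4 = (s7² − r·s4·s7) / (s4² + s7² − 2·r·s4·s7), and w7 = 1 − w4.

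The documents give no SDs or correlations for these scores, so the inputs below are assumptions. Take d4 = -0.2 and d7 = -1.0.

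- s4 = s7 = 1.5, r = 0.6: w4 = w7 = 0.5. Result: 0.5 × (-0.2) + 0.5 × (-1.0) = -0.60.
- s4 = 1.2, s7 = 1.8, r = 0.6: w4 = (3.24 − 1.296) / (4.68 − 2.592) = 1.944 / 2.088 = 0.931 and w7 = 0.069. Result: -0.26.
- s4 = 1.2, s7 = 1.8, r = 0.7: w4 = (3.24 − 1.512) / (4.68 − 3.024) = 1.728 / 1.656 = 1.043 and w7 = -0.043. Result: -0.17.

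The Visit 7 difference is -1.0 in all three cases. In the last, Visit 7 even receives a small negative weight. If instead d4 = d7 = -0.5, all three settings return -0.5. The written contrast therefore equals the Visit 7 difference whatever the covariance only if the class difference is constant over visits.

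**The anchor cut.** None, mild, moderate and severe are the four PGIS levels, so the cut is the median baseline score of everyone reporting any symptoms. At most half of them can lie below it, and ties go to the upper class. In simulations with assumed distributions, the mean share below the cut was 50% for continuous scores, about 48% for integer scores on a 13–65 range and about 46% on a 5–25 range. It did not exceed 50%.

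**The case against.** The strongest reply is that this is a single drafting slip, to be settled by a query and a one-phrase edit. Section 7.3.9.3 also tabulates change from baseline by class at each visit and plots its cumulative distribution by class at Visit 7, so the Visit 7 comparison is available descriptively. That stands, and it keeps the point small. It does not rescue the model: the only contrast with an interval and a p-value is still the wrong one, and the blinding contradiction is plain on the page. By the same token, a reader might infer that the blind would be broken. The documents show a contradictory instruction, not a plan to release codes.

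A second tempting inference is that the baseline covariates should go, because the anchor class is cut from the same baseline score. That would do harm. Suppose nobody truly changes and the score has reliability R. Then expected change given baseline is −(1 − R) times the patient's distance from the mean. For a normal score split at its median, the class means differ by 2 × √(2/π) = 1.596 SD, so the unadjusted class difference in change is −(1 − R) × 1.596 SD. This is -0.16 SD at R = 0.9, -0.40 at 0.75 and -0.64 at 0.6 (assumed reliabilities). Simulation agreed and put the baseline-adjusted difference within 0.01 SD of zero. Nor does adjustment always remove a class difference when change varies smoothly with baseline. That is exact only for a linear relation; in simulated non-linear cases the adjusted effect ranged from -0.22 to +0.48 residual SD.

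A third inference is that the cut fails because it detects only about half of patients with symptoms. The arithmetic is right, but sections 7.3.9 and 7.3.9.2 aim to separate low from high, or significant, burden. They do not set out to detect any symptom, so sensitivity for PGIS mild or worse is not the plan's target. A cut between none and mild would answer a different question.

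**Conclusion.** The point holds as a minor error of model specification. The treatment-by-visit term contradicts the blinded, pooled basis of the analysis, and the missing class-by-visit term means that the Visit 7 class difference is not estimated. The size of the distortion is unknown. The -0.60 to -0.17 against a true -1.0 rests on assumed differences, SDs and correlations and on both visits being observed; there is no distortion if the class effect is constant over visits. That the wording is an incomplete edit of the clinical SAP model is inferred from the match between the two sentences.

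The analysis is exploratory and is described as iterative. The treatment comparisons listed in PRO SAP sections 5.5 to 5.8 do not use symptom class, and no primary or secondary endpoint depends on it. The median cut earns only a remark on labelling: up to about half of patients with PGIS mild or worse fall in a class called non-symptomatic. This applies to the anchor method, not to the clusters.

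**What to change.** In PAP section 7.3.9.3, replace the treatment group-by-visit interaction with a symptom class group-by-visit interaction. State that the class least squares means and their difference will be reported at Visit 7, with the Visit 4 contrast alongside if the pattern over time is of interest. Keep the baseline and baseline-by-visit covariates. If adjustment for treatment was intended after all, say so and schedule that model after unblinding; class-by-visit is needed in either case.

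In section 7.3.9.2, call the lower class low symptom burden, which section 7.3.9 already uses, and drop the label non-symptomatic.

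The cost is one phrase, one label and a line or two of program. With two classes and two visits the new term adds (2 − 1) × (2 − 1) = 1 parameter. The treatment term removed had (4 − 1) × 2 = 6, for four arms and two visits with no treatment main effect. The Visit 7 contrast may have a somewhat wider interval than one shared across visits, which is the price of estimating the intended quantity.
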